4.1 Endpoints

4.1.1 Part A

The primary endpoint for safety is the incidence of AEs (overall or grouped as neurological, psychiatric or cardiovascular).

The hypothesis for the primary endpoint for safety is that ABvac40 will be safe for human administration, according to the observed pattern of AEs. The trial will be considered satisfactory if the pattern of AEs (overall or grouped as neurological, psychiatric or cardiovascular) is consistent with a good safety and tolerability profile of ABvac40 for human administration at the final visit.

Additionally, the following secondary safety endpoints will be evaluated including:

- number of withdrawn patients due to adverse events (AEs)
- number of withdrawn patients due to other causes
- number of serious adverse events (SAEs)
- number of clinically significant changes in physical and neurological examination
- number and type of concomitant medications
- number of clinically significant changes in vital signs (blood pressure, heart rate, respiratory rate, body temperature), body mass (weight, height).
- number of clinically significant changes in brain MRI
- number of clinically significant changes in electrocardiogram (EKG)
- number of clinically significant changes in analytical haematology, biochemistry, coagulation, serology and urine test strip results.

The primary efficacy endpoint is the average maximal increment ($M\Delta$) of anti-A β 40 antibody signal (OD in ELISA) in each subject with regard to the pre-treatment visit (either V0 or V1).

For the primary efficacy analysis, the trial will be considered successfully confirmatory regarding efficacy (immunogenicity) of ABvac40 if the average maximal increment ($M\Delta$) of anti-A β 40 antibody signal (OD in ELISA) in the verum group is >0 OD than the average $M\Delta$ in the placebo group. For the secondary efficacy analysis, the trial will be considered satisfactory if the difference of the average maximal increment ($M\Delta$) of anti-A β 40 antibody signal (OD in ELISA) in the treated group is > 1.778 OD than the average $M\Delta$ in the placebo

group; the difference that was reached between both groups in the phase I clinical trial of ABvac40.

Additionally, the following secondary efficacy endpoints will be evaluated including:

- Characterization of the immune response:
 - o Levels of anti-KLH and anti-A β 42 antibodies in plasma
 - o Level of anti-A β 40 antibodies in CSF

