8.2.5 EKG

An electrocardiogram (EKG) will be performed at visits V0, V16, V21, V23 and V25 during Part A and at visits V16B, V21B and V22B during Part B (and PDV, if applicable). All EKGs, will be assessed centrally by the Medical Advisor. Any new finding or worsening of a previous finding will be recorded in the subject's eCRF as an AE.

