9.1.3.2 Secondary Safety Analysis

The safety and tolerability analysis will be based on the safety population, comprising all subjects who took at least one dose of study medication.

Withdrawal criteria (discontinuation decision):

Withdrawal criteria will be summarized using descriptive statistics.

Number of withdrawn patients due to adverse events (AEs); reason for withdrawal:

The number and percentage of patients (in each treatment group) prematurely discontinuing study treatment due to an AE will be tabulated by SOC and PT. Listings of patients with AEs leading to discontinuation and individual narrative summaries for these cases will be provided.

Serious adverse events (SAEs)

The number and percentage of patients in each treatment group reporting at least 1 occurrence of a SAE for each unique SOC and PT will be tabulated. SAEs will be also tabulated by the relationship to study medication in treatment groups as assessed by the investigator. Listings of patients with SAEs (and deaths) and individual narrative summaries for these cases will be provided.

Physical and neurological examination

Physical findings (normal and abnormal) will be listed for each clinical trial subject. Any clinically significant abnormality developed by individual during the clinical trial and not already present at baseline will be reported as an AE.

Physical and neurological examination data will be summarized in tables.

Concomitant medication

Concomitant medication and concomitant therapy will be summarized as number of patients being treated with each type of medication/therapy classified according to ATC level 3 and World Health Organization (WHO) Drug Dictionary preferred term.

Vital signs and anthropometric data

Vital signs (blood pressure, heart rate, respiratory rate and body temperature) and anthropometric data (body mass index, weight and height) will be summarized together with changes from baseline.

Brain MRI

Brain MRI findings will be listed for each clinical trial subject and summarized in tables.

ECG

Overall interpretation of ECG results (i.e. normal or abnormal and clinical significance) as well as ECG findings will be summarized in tables.

Laboratory safety assessments

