4.1.2 Secondary Safety Variables

- Withdrawal criteria (study continuation decision)
- Physical examination:

Complete physical examinations will be performed at all face-to-face visits. These assessments include examination of the neck (including thyroid), eyes, ears, throat, abdomen, skin/mucous membranes, and cardiovascular, respiratory, genito-urinary, and musculoskeletal systems.

- Neurological examination:
Neurological examinations are performed at all face-to-face visits. These assessments include cortical function, cranial nerves, motor function, reflexes, sensory function, gait, and posture.

- Concomitant medication
Each medication will be coded to Anatomical Therapeutic Chemical (ATC) classification codes using the World Health Organization Drug classification Dictionary (WHO-DD), version WhoDrug B2 2017Q3 and defined as either a prior or concomitant medication, depending on the start and end dates of the medication, relative to the date of first dose of study treatment.

Prior medications will be defined as any medication ended prior to the first dose of study treatment.

Concomitant medications will be defined as any medication started on or after the start of study treatment or any medication taken prior to the start of study treatment and continued after the start of study treatment.

- Vital signs:
The following vital signs parameters will be monitored: blood pressure, heart rate, respiratory rate, body temperature).

- Electrocardiogram (ECG):
The following ECG parameters will be recorded: HR, PR interval, QRS and QT.

- Laboratory Assessments:
Laboratory assessments will be performed for the following: Hematology, Toxicology (reactive protein), Biochemistry, Coagulation, Serology and Urine sampling. Appendix 9.3 provides a list of that laboratory test parameters that will be recorded.

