7.3.6 Electrocardiogram

ECG parameters HR, PR interval, QRS and QT will be summarized by study visit and treatment sequence group for Part A and Part B.

Each of the ECG parameters were classified as normal or abnormal at each visit. Using this information, the overall ECG finding at each visit will be categorized as:

- Abnormal – if any one of the individual ECG parameters are abnormal at that visit
- Normal – if all the individual ECG parameters are normal at that visit
- Missing – if at least one of the individual ECG parameters is missing and none of the non-missing ECG parameters are abnormal.

These categorizations of ECG findings will be summarized using a shift table, presenting the count and percentage of patients whose categorizations change or remain the same from baseline to each post-baseline scheduled visit. The shift table will be presented by treatment sequence and will include “Missing” as a result category

A listing of ECG findings and results will also be presented.

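### SAP 7.3.6 derives the overall ECG finding from HR, PR, QRS and QT flags alone, so it can count an abnormal tracing as Normal and leaves the protocol's ECG safety endpoint without a planned table

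*SAP*

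**What the plan says.** **Protocol.** Section 4.1.1 lists among the secondary safety endpoints the "number of clinically significant changes in electrocardiogram (EKG"). Section 9.1.3.2 then states the analysis: "Overall interpretation of ECG results (i.e. normal or abnormal and clinical significance) as well as ECG findings will be summarized in tables". Section 8.2.5 says that all EKGs "will be assessed centrally by the Medical Advisor" and that any new or worsened finding is recorded as an adverse event. The synopsis (Study Assessments and Procedures) and section 8.2 except visit V22B from the central assessment; section 8.2.5 does not.

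**SAP.** Section 4.1.2 defines the ECG variables: "The following ECG parameters will be recorded: HR, PR interval, QRS and QT". Section 7.3.6 repeats the same four: "ECG parameters HR, PR interval, QRS and QT will be summarized by study visit and treatment sequence group". It says that each was classified as normal or abnormal at each visit, and continues: "Using this information, the overall ECG finding at each visit will be categorized as" Abnormal if any of the four is abnormal, Normal "if all the individual ECG parameters are normal at that visit", and Missing if at least one is missing and none of the rest is abnormal. The shift table from baseline uses these categories only. The section closes with: "A listing of ECG findings and results will also be presented".

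**The concern.** The protocol plans to report a reading of the whole tracing together with its clinical significance. The SAP reports a composite of four parameter flags and gives it the name of an overall finding. These are different quantities. A tracing can be read as abnormal for a reason that none of the four parameters captures, and the composite has no way to record that.

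The protocol's clinical-significance dimension also disappears from the ECG tables. The SAP has not dropped it in general: the physical and neurological examination shift tables (7.3.2, 7.3.3) and the laboratory shift tables (7.3.7) all separate clinically significant from non-significant abnormalities. Of these shift tables, only the ECG one does not.

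Safety is a primary objective of Part A, and cardiovascular events are one of the three named adverse event groupings. A reader of the study report would take a table of overall ECG findings at face value.

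**Working it through.** No stated figure is to be reproduced. The check is a comparison of the texts and a trace of the SAP rule.

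**1. What is promised and what is specified**

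| Item | Protocol | SAP |
|---|---|---|
| Overall interpretation, normal or abnormal | Tabulated (9.1.3.2) | Replaced by a category derived from HR, PR, QRS and QT flags (7.3.6) |
| Clinical significance | Tabulated (9.1.3.2); endpoint (4.1.1) | No category and no count |
| ECG findings | Tabulated (9.1.3.2) | Listing only (7.3.6) |
| Declared as a change | – | Not in 9.2 |

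SAP 1.1 gives the SAP precedence where it differs from the protocol, so the derived rule is the one that will be run.

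**2. Trace of the rule**

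| Flags on the four parameters | Reading of the whole tracing | SAP category |
|---|---|---|
| All normal | Normal | Normal |
| All normal | Abnormal for another reason | **Normal** |
| At least one abnormal | Any | Abnormal |
| At least one missing, none abnormal | Any | Missing |

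In the second row the Abnormal rule cannot fire because no flag is abnormal, and the Missing rule cannot fire because no flag is missing. The Normal rule is met. This follows from the wording alone and needs no assumption about rates.

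**3. Visits affected**

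Scheduled ECGs are at V0, V16, V21, V23 and V25 in Part A and at V16B, V21B and V22B in Part B: 5 + 3 = 8. V0 is the only scheduled ECG before the first dose, so it is the baseline, and up to 8 − 1 = 7 post-baseline visits enter the shift table. The rule applies to the baseline and to all seven.

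**4. Size**

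Let *p* be the proportion of tracings read as abnormal and *f* the share of those with all four parameters flagged normal. If every other abnormal reading carries at least one abnormal flag, the table shows *p*(1 − *f*) as Abnormal and hides *pf*. Neither document gives *p* or *f*. The shortfall can lie anywhere from none (*f* = 0) to every abnormal reading (*f* = 1).

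**5. What reaches other outputs**

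- A new or worsened finding is recorded as an adverse event (Protocol 8.2.5). Treatment-emergent events are tabulated by SOC and PT (SAP 7.2.1).
- An abnormality already present at baseline and unchanged is not covered by that rule. If it lies outside the four parameters, it is Normal in the shift table throughout and can be seen only in the listing.
- Adverse events are tabulated by treatment group and the ECG shift table by treatment sequence (SAP 3). A reader cannot readily set one against the other when they disagree.

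**The case against.** The strongest reply is that little is lost. New or worsened findings become adverse events whether or not they are clinically significant, which is a wider net than the endpoint, and the ECG listing is kept. The table is descriptive: no hypothesis, success criterion or monitoring rule rests on it. This stands, and it limits the consequence. It does not supply what the protocol planned. The adverse event tables do not separate clinically significant ECG changes, and a listing is not a table.

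A second reply concerns the flags. SAP 7.3.6 does not say who set them or against what range, so a reader of the tracing may have marked a parameter abnormal for wider reasons. That could make the second row of the trace less frequent. The SAP does not require it, so the gap remains.

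A third reply is practical. The eCRF content lists in Protocol 4.9 name only the electrocardiogram, without a field for overall interpretation or significance. The database may hold parameter flags and nothing more. The documents do not settle this, and the fix has to allow for it.

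A reader might infer more than the text supports:

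- *Every rhythm or repolarisation abnormality is tabulated as Normal.* This holds only when all four parameters are flagged normal. Neither document names such abnormalities as recorded items; they are examples of what could lie outside the four.
- *A tracing with no measurable PR is always Missing.* It is Missing only if PR is recorded as missing and none of the other three is abnormal. The SAP does not say how an unmeasurable PR is flagged.
- *The endpoint cannot be produced at all.* What can be said is that no specified table produces it. Whether the data would allow it is not stated.

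**Conclusion.** The point holds as a wrong rule and an undeclared departure from the protocol. Followed exactly, SAP 7.3.6 counts as Normal any tracing that is read as abnormal while HR, PR, QRS and QT are all flagged normal. No specified SAP table gives the overall interpretation with clinical significance, the ECG findings, or a count of clinically significant ECG changes. SAP 9.2 is silent on this.

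The consequence is moderate: a descriptive safety table that can mislead, and a named secondary safety endpoint with no planned output. The primary safety analysis of adverse events and the immunogenicity analysis are untouched. The frequency of misclassification is unknown, and any percentage would be a guess. The conclusion rests on the SAP wording as it stands and on SAP 1.1 giving it precedence. It should be corrected before the ECG tables are produced.

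**What to change.** 1. In SAP 7.3.6, build the shift table on the recorded overall interpretation, with the categories normal, abnormal not clinically significant, abnormal clinically significant, and missing. Use the central assessment where one was made and the site's recorded interpretation at V22B.
2. Reconcile the synopsis and Protocol 8.2 with 8.2.5 on whether V22B is centrally assessed, so that the source of the interpretation at that visit is settled.
3. Add a table of ECG findings by treatment sequence and visit, and a count of clinically significant changes from baseline for the endpoint in Protocol 4.1.1.
4. Keep the four-parameter category as a supplementary summary under a name that says what it is.
5. If the overall interpretation was not captured in the database, state and justify this in SAP 9.2, label the table as based on HR, PR, QRS and QT only, and do not call it the overall ECG finding.

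**Cost.** If the interpretation was captured, the cost is a SAP text change, a revised shift-table shell and added summaries, with no new data collection. If it was not, the cost is a declaration in SAP 9.2 and a new table title, and the endpoint in Protocol 4.1.1 must be reported as not tabulated. The eCRF should be checked first, because the documents do not show which case applies.

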7.3.7 Laboratory Assessments

Appendix 9.3 provides a list of laboratory assessments that will be summarized.

Continuous parameters will be summarized by scheduled visit and treatment sequence group for Part A and Part B. The summaries will include change from baseline to each scheduled post-baseline visit.

In addition, the laboratory results will be categorized as

- Normal
- Abnormal Low – Clinically Significant (CS)
- Abnormal Low – Not Clinically Significant (NCS)
- Abnormal High – CS
- Abnormal High – NCS

based on laboratory normal ranges and the categorization of clinical significance of out of range results. These categorizations will be summarized using shift tables, presenting the count and percentage of patients whose categorizations change or remain the same from baseline to each post-baseline scheduled visit for each parameter. Shift tables will be presented by treatment sequence and will include “Missing” as a result category.

Laboratory results with discrete or categorical results will be summarized using frequency tables presenting the count and percentage of patients with results within each category of result, by scheduled visit and treatment sequence for Part A and Part B.

A listing of laboratory results will also be presented.

9 APPENDICES

9.1 Imputation rules

9.1.1 AE date imputation

The following rules will be applied to impute AE start/end dates when partial AE start/end dates have been recorded. The imputed dates will be used for the determination of TEAEs only. The original partial AE dates will be presented in data listings.

AE start date imputation:

AE start date imputation will be based on a comparison of the partial AE start date and the treatment start date. [Table 2-1](#) presents the notation that will be used to describe the rules for imputation of partial AE start dates.

Table 2-1 Notation for imputation of partial AE start dates

	Year	Month	Day
Partial AE start date	YYYY	MON	Not used
Study treatment start date	TRTY	TRTM	Not used

[Table 2-2](#) presents a matrix of rules for the imputation of AE start dates.

Table 2-2 AE start date imputation

	MON MISSING	MON < TRTM	MON = TRTM	MON > TRTM
YYYY MISSING	NULL Uncertain	NULL Uncertain	NULL Uncertain	NULL Uncertain
YYYY < TRTY	(D) = 01JULYYYY Before Treatment Start	(C) = 15MONYYYY Before Treatment Start	(C) = 15MONYYYY Before Treatment Start	(C) = 15MONYYYY Before Treatment Start
YYYY = TRTY	(B) = TRTSTD+1 Uncertain	(C) = 15MONYYYY Before Treatment Start	(A) = TRTSTD+1 Uncertain	(A) = 01MONYYYY After Treatment Start
YYYY > TRTY	E = 01JANYYYY After Treatment Start	(A) = 01MONYYYY After Treatment Start	(A) = 01MONYYYY After Treatment Start	(A) = 01MONYYYY After Treatment Start
Before Treatment Start	Partial indicates date prior to Treatment Start Date			
After Treatment Start	Partial indicates date after Treatment Start Date			
Uncertain	Partial insufficient to determine relationship to Treatment Start Date			
LEGEND:				

MON MISSING	MON < TRTM	MON = TRTM	MON > TRTM
NULL	No imputation		
(A)	Max(01MONYYYY,TRTSTD+1)		
(B)	TRTSTD+1		
(C)	15MONYYYY		
(D)	01JULYYYY		
(E)	01JANYYYY		

1. If the AE start date year value is missing, the date uncertainty is too high to impute a rational date. Therefore, if the AE year value is missing, the imputed AE start date is set to NULL (i.e. no imputation).
2. If the AE start date year value is less than the treatment start date year value, the AE started before treatment. Therefore:
 - a. if the AE year is less than the treatment year and the AE month is missing, the imputed AE start date is set to the mid-year point (01JulYYYY).
 - b. else, if the AE year is less than the treatment year and the AE month is not missing, the imputed AE start date is set to the mid-month point (15MONYYYY).
3. If the AE start date year value is greater than the treatment start date year value, the AE started after treatment. Therefore:
 - a. if the AE year is greater than the treatment year and the AE month is missing, the imputed AE start date is set to the year start point (01JanYYYY).
 - b. else, if the AE year is greater than the treatment year and the AE month is not missing, the imputed AE start date is set to the month start point (01MONYYYY).
4. If the AE start date year value is equal to the treatment start date year value:
 - a. and the AE month is missing or the AE month is equal to the treatment start month, the imputed AE start date is set to one day after treatment start.
 - b. else, if the AE month is less than the treatment start month, the imputed AE start date is set to the mid-month point (15MONYYYY).
 - c. else, if the AE month is greater than the treatment start month, the imputed AE start date is set to the start month point (01MONYYYY).

Imputed AE date flag

If the year of the imputed date is not equal to YYYY then imputed date flag = Y, else if month of the imputed date is not equal to MON then imputed date flag = M, else if day of the imputed date is not equal to day of original date then imputed date flag = D, else imputed date flag = null.

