7.2 Summary of Primary Safety Outcome

7.2.1 Adverse Events

Adverse events will be classified as Treatment-Emergent AEs (TEAEs) or non-Treatment-Emergent AEs (non-TEAEs), based on the comparison of the AE onset date/time with the start date/time of study treatment.

- A TEAE will be defined as an AE which starts or worsens in severity during or after the first administration of study treatment.
- A non-TEAE will be defined as an AE which starts or worsens in severity prior to the start of the first administration of study treatment.

The following algorithm will be used to identify the treatment group under which each AE will be summarized:

For SAESIs:

- AEs that start or worsen in severity at any time after a patient's first dose of ABvac40 will be associated with the ABvac40 treatment group.
- AEs that start or worsen in severity after first dose of Placebo, but before first dose of ABvac40, will be associated with the Placebo treatment group

For non-SAESIs:

- For patients randomised to the ABvac40 arm Part A / Placebo+Booster arm Part B treatment sequence:
 - AEs that start or worsen in severity at any time during or after a patient's first dose of study drug in part A and prior to their booster ABvac40 vaccination will be associated with the treatment received at their last injection prior to the AE.
 - AEs that start or worsen in severity during or after a patient's booster ABvac40 vaccination will be associated with the ABvac40 treatment group.
- For patients randomised to the Placebo arm Part A / ABvac40 arm Part B treatment sequence:
 - AEs will be associated with the treatment received at their last injection prior to the AE.

For the purposes of classifying AEs as treatment emergent and to assign treatment groups, partial AE start and end dates will be imputed to allow comparison with the study treatment date start and end dates. Section 9.1.1 below presents the imputation rules. Note, the imputed dates will be used for classification purposes and treatment group assignment purposes only and the original partial AE dates will be presented in data listings.

An overall summary of AEs will be presented by treatment group, by providing counts and percentages of patients with any: TEAE, non-TEAE, Treatment related TEAEs, TEAE leading to treatment discontinuation, TEAEs leading to death, Treatment-Emergent Serious AE (TESAE), Treatment-

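### SAP 7.2.1 and 9.1.1 disagree on the use of imputed adverse event dates, and the rules can place partially dated events on the wrong side of the V1B and V13B treatment switches

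*SAP*

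**What the plan says.** SAP 7.2.1 gives imputed dates two uses: "For the purposes of classifying AEs as treatment emergent and to assign treatment groups, partial AE start and end dates will be imputed". It then repeats that "the imputed dates will be used for classification purposes and treatment group assignment purposes only". The appendix allows one use: "The imputed dates will be used for the determination of TEAEs only".

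On method, SAP 9.1.1 states: "AE start date imputation will be based on a comparison of the partial AE start date and the treatment start date". It refers to no later dose. The rules for a known year are:

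- In the treatment-start month, or in the treatment-start year with the month missing, the date becomes the day after treatment start.
- In any later month, the date becomes the first of that month.
- In a later year with the month missing, the date becomes 1 January.
- Dates before treatment start go to mid-month or mid-year.

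SAP 7.2.1 then allocates each event to ABvac40 or placebo:

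- **Delayed-start sequence** (placebo in Part A, ABvac40 in Part B), events not of special interest: "AEs will be associated with the treatment received at their last injection prior to the AE".
- **ABvac40-first sequence** (placebo in Part B except the V13B booster), events not of special interest: last injection received up to the booster, and ABvac40 from the booster on.
- **Serious events of special interest (SAESIs)**: ABvac40 at any time after a first ABvac40 dose, otherwise placebo.

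SAP section 3 presents AE summaries across Parts A and B in these two columns.

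**The concern.** The two sections cannot both hold. If 9.1.1 governs, no rule assigns a partially dated event to a treatment. If 7.2.1 governs, a rule built to answer one question (before or after the first study dose?) is used to answer another (before or after a change of treatment?). It protects the treatment start date but not V1B or V13B, where patients change treatment.

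AEs are the primary safety variable. In a two-column table pooled over both parts, date order alone decides the column for a patient who has received both products. An event that follows an ABvac40 dose can therefore be reported as a placebo event, and the reverse can also occur.

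**Working it through.** The documents give no figure on this point, so there is none to reproduce. The check applies the SAP rules to known dates.

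**Anchor.** SAP 2.1.2 places V1B at least 18 months after the start of Part A, so V1B always falls in a later calendar year. With the Part A start as anchor, every day-missing Part B onset becomes the first of its month.

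**Illustrative dates.** Part A starts 10 Sep 2018 and V1B is 14 Sep 2020. V10B (day 84) is then 7 Dec 2020 and V13B (day 112) is 4 Jan 2021.

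- Delayed start, true onset 20 Sep 2020, day missing: imputed 1 Sep 2020. The last injection is Part A placebo, so the event counts under placebo.
- ABvac40-first, non-SAESI, true onset 10 Jan 2021, day missing: imputed 1 Jan 2021. The last injection is the V10B placebo, so the event counts under placebo.
- Mirror case: ABvac40-first, non-SAESI, true onset 20 Sep 2020 after the placebo V1B dose: imputed 1 Sep 2020. The last injection is Part A ABvac40, so the event counts under ABvac40.

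**Share misplaced.** Assumptions: 600 consecutive Part A start dates from 1 Feb 2018; V1B at day 560; doses in each part on days 0, 28, 56, 84, 112 and 294; true onset spread evenly over days 1–14 or 1–28 after the dose. An imputed date equal to the dose date counts as after the dose. Percentages are of partially dated events only.

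| True onset after | Missing | Wrong column | Anchor = Part A start (14 d / 28 d) | Anchor = V1B (14 d / 28 d) |
|---|---|---|---|---|
| V1B, delayed start, any event | day | placebo | 72% / 49% | 0% / 0% |
| V13B, ABvac40-first, non-SAESI | day | placebo | 73% / 49% | 73% / 49% |
| V13B, ABvac40-first, SAESI | day or month | placebo | 0% / 0% | 0% / 0% |
| V1B placebo, ABvac40-first, non-SAESI | day | ABvac40 | 72% / 49% | 0% / 0% |
| V1B, delayed start, any event | month | placebo | 97% / 95% | 0% / 0% |
| V13B, ABvac40-first, non-SAESI | month | placebo | 37% / 37% | 97% / 95% |
| V1B placebo, ABvac40-first, non-SAESI | month | ABvac40 | 97% / 95% | 0% / 0% |

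**Hand check, day missing.** The average month has 365/12 = 30.42 days. An event k days after a dose is misplaced if it falls in the dose month and the dose was not on the 1st, with probability about (30.42 − k − 1)/30.42.

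- Days 1–14 (mean k = 7.5): (30.42 − 8.5)/30.42 = 0.72.
- Days 1–28 (mean k = 14.5): (30.42 − 15.5)/30.42 = 0.49.

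**Hand check, month missing, V13B, Part A anchor.** The event moves to placebo only if 1 January falls between V1B and V13B, which are 112 days apart. The 600 V1B dates span two year-ends: 2 × 112/600 = 37%. Otherwise 1 January precedes V1B too, the last injection is Part A ABvac40, and the event stays under ABvac40.

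**The case against.** **Partial dates should be rare.** Onset date and time is a required field (Protocol 8.3.8). Patients keep a diary (8.2.7), are telephoned within the first week after each vaccination and are seen at two weeks. Missing data are queried. This stands and limits the size. The original partial dates also stay in the listings, so affected events can be found.

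**The start date may be part-specific.** SAP section 3 defines a separate Day 1 for Part B. It does so for study days in listings, and 9.1.1 does not cite it; the TEAE definition in 7.2.1 points to the first administration. If 9.1.1 did mean the Part B start, the V1B errors would vanish in both sequences. The day-missing booster error would stay at 73% and 49%, because no start date protects V13B.

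**SAESI exposure is small.** Amyloid-related imaging abnormalities are found on MRI, so the date of the finding should be known, and the first scheduled MRI after V1B is V9B at week 10. This stands: a delayed-start SAESI is exposed only if it is detected otherwise and has a partial onset date.

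**Part B is exploratory and Part A is reported separately.** This also stands. Each patient's planned treatment is constant within Part A, so the imputation cannot move a Part A event between arms. The error reaches the pooled descriptive tables only.

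**A stronger reading is tempting:** that the rule makes the vaccine look safer. The two switches to ABvac40, viewed alone, suggest it. The documents do not support it, because the same rule pulls events after the placebo V1B dose back into ABvac40.

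**Conclusion.** The point holds in a limited form. SAP 7.2.1 and 9.1.1 contradict each other on the use of imputed dates. If 7.2.1 governs, partially dated events near V1B and V13B can be put in the wrong treatment column of the pooled AE summaries. The V1B part rests on the Part A start being the anchor, which is the natural reading; the V13B part holds on either reading.

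Among day-missing events the share misplaced is about 72–73% for onset within 14 days of the dose and 49% within 28 days, under the timing assumptions above. The absolute number cannot be stated, because the documents do not say how many dates are partial; it is probably small.

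A reader should not infer that every post-booster event is misassigned: SAESIs are not, and with the month missing about 63% (100% − 37%) stay under ABvac40 on the Part A anchor. Nor should a reader infer that the randomised Part A comparison is affected, or that the net bias favours ABvac40. The error runs both ways and its balance is unknown. The correction is worth making before database lock, but it does not threaten the trial's main conclusions.

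**What to change.** 1. Amend SAP 9.1.1 to agree with 7.2.1 that imputed dates also assign the treatment group.
2. State which treatment start date is meant, and add the doses where treatment switches as anchors: V1B in both sequences and V13B in the ABvac40-first sequence.
3. For a switch to ABvac40 (V1B in delayed start, V13B in ABvac40-first): if the recorded part of the onset date, and any end date, allow onset on or after that dose, impute the later of the first of the month (or 1 January if the month is missing) and the day after the dose, and assign the event to ABvac40. In the examples this gives 15 Sep 2020 and 5 Jan 2021, both under ABvac40.
4. For the placebo V1B dose in the ABvac40-first sequence, state that ambiguous events stay under ABvac40.
5. Declare the convention as conservative for safety.

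By construction, no partially dated event that truly follows one of these switches to ABvac40 is then counted under placebo. The cost is a few lines of SAP text and one programming change. The downside is that a few pre-dose or placebo-period events will be counted under ABvac40.
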